5.5.2 Secondary Analysis: SCCS with both Pre- and Post-vaccination Control Intervals

Eligible vaccinees should meet the following inclusion/exclusion criteria.

Inclusion criteria:

The same as the primary analysis (Section 5.5.1).

Exclusion criteria:

The same as the primary analysis (Section 5.5.1) with one additional criterion below.

- (vi) Had a diagnosis of the AESI during 14 days prior to COVID-19 vaccination or different pre-exposure intervals in sensitivity analyses.

5.5.3 Exploratory Analysis: SCRI with a Pre-vaccination Control Interval

Eligible vaccinees should meet the following inclusion/exclusion criteria:

Inclusion criteria:

The same as the primary analysis (Section 5.5.1).

Exclusion criteria:

The same as the secondary analysis (Section 5.5.2) except that the following criterion is not required.

- (ii) Does not contribute follow-up time to both risk and control intervals. If individuals disenroll, or reach the end of the study period during the risk window prior to accumulating any time for post-vaccination control intervals, they will be excluded.

5.6 Time-varying Confounding

Time-varying confounding may be of concern in the SCCS design with longer control intervals during the study observation period. Some AESI, including AMI, exhibit seasonal trends. In addition, given that COVID-19 has been associated with cardiovascular disorders, and the risk of exposure to COVID-19 varies throughout the study period, the risk of related cardiovascular AESI may vary during the study period.^{15,16} Adjustment for time-varying confounding will be considered based on their association with the individual AESI and addressed using statistical models if strong time-varying confounding exists. The SCRI design is less susceptible to time-varying confounding given the discrete and relatively short risk and control intervals.

5.7 Statistical Analysis

5.7.1 Descriptive Statistics

Descriptive statistics will present counts and percentages of AESI overall and by risk/control interval for the following covariates, where available in the database:

- Demographics: age, sex, race/ethnicity, region, urban/rural, dual eligibility status, area deprivation index (ADI), nursing home residency status
- Cases that died in the observation period
- Cases that received an influenza vaccine at the same time as the COVID-19 vaccine
- Cases that received other vaccines (e.g., influenza and pneumococcal) in the risk or control intervals for each dose
- Cases with a history of a medically attended COVID-19 infection, defined by the ICD-10-CM codes U07.1 (COVID-19)
- Cases affected by the inclusion and exclusion criteria used to construct the study population
- Plot occurrence of AESIs by day and by vaccine brand during the observation period, e.g., stacked strip plots
- Risk factors for the AESI. Based on signal evaluation investigations in RCA, the following risk factors are considered, but not limited to:
 - Hospitalization (prior 6 months)
 - Prior hospitalization for other AESI (e.g. in AMI analysis, hospitalization for stroke)
 - Neurological/Neurodevelopmental Conditions

- Hypertension
- Diabetes
- COPD/Asthma
- Atrial Fibrillation
- Charlson Comorbidity Index

5.7.2 Primary Analysis: SCCS with Post-vaccination Control Intervals

For the primary self-controlled analysis, the risk of the AESI following any dose will be evaluated, without distinguishing between dose numbers. This analysis will compare the AESI rates in the risk and control intervals using a conditional Poisson regression model. For two-dose COVID-19 vaccines, the model assumes constant risk throughout each risk window, regardless of how close together the two doses may be administered (i.e., no additive risk from overlapping risk windows). Sensitivity analysis (Section 5.7.2.1) is planned to evaluate the robustness of this assumption. Under the assumption of constant risk, the following model will be fit:

$$\log(E(Y|X)) = \beta_1(\text{risk_interval}) + \log(t) + \text{strata}(\text{patient_id})$$

Y = AESI
risk_interval = binary term indicating AESI occurrence in risk interval
t = interval
patient_id = term identifying the patient

Under this model, the null and alternative hypotheses can be written as:

$$H_0: e^{\beta_1} = 1 \quad H_a: e^{\beta_1} \neq 1$$

where e^{β_1} will be interpreted as the rate ratio for the AESI in the risk interval compared to the control intervals. Thus, statistical significance of the coefficient on the risk interval variable at a pre-specified level will indicate a statistically significant association between COVID-19 vaccination and the AESI. Statistical significance will be determined using 95% confidence intervals of rate ratios and two-sided p-values ($p \leq 0.05$).

The study will estimate the AR (per million vaccinations). The number of excess AESI cases due to the vaccine will be directly derived from the conditional Poisson regression model, defined as the difference between the sum of the model fitted values (i.e., model predicted number of cases), and the sum of the expected cases if there were no vaccination (i.e., all observed time is treated as control time). The unadjusted AR is the excess number of AESI cases divided by the number of eligible vaccinations (or eligible follow up dose-years). The standard error (SE) of the unadjusted AR is estimated by bootstrap resampling 10,000 times.¹⁷ For each iteration, the study will sample the beneficiaries with AESI with replacement and repeat the AR calculation. The SE is calculated as the square root of the variance of the 10,000 AR values. The AR following COVID-19 vaccination may be compared to the AR following other vaccinations and other AESI-triggering exposures. While the unadjusted ARs are directly obtained from the primary claims-based analysis and secondary chart-confirmed analysis, they might not be truly representative of the underlying AESI risk. Thus, a positive predictive value (PPV)-adjusted AR may be calculated following the completion of the medical record review (see Section 6 for the medical record review process).

When sample size permits, subgroup analyses by age group, sex, race/ethnicity, and nursing home residency status will be performed.

[figure not shown]
5.7.2.1 *Sensitivity Analyses for the Primary Analysis*

To evaluate potential time-varying confounding given the length of observation period, the study will assess the association of time-varying risk factors with the AESI and adjust for the changing risk of the AESI associated with the major time-varying risk factors. For example, historical incidence rates of AMI have exhibited seasonality. The following methods will be explored to estimate the baseline risk curve as an offset term to be included in the conditional Poisson regression model.

- From a similar population during the same calendar months in previous years. However, health care utilization was reported to be affected in the early pandemic¹⁸, and historical monthly rates may not be comparable.
- From post-vaccination control intervals if sample size permits.

To evaluate the assumption of constant risk throughout each risk interval for two-dose COVID-19 vaccines, potential differences in risk will be stratified by vaccine dose if sample size permits. Analyses will be restricted to vaccinations where the administration codes are concordant with the order of vaccination procedure codes. The overall risk interval will be categorized as 1) dose 1 only; 2) overlapping dose 1 and dose 2, where risk intervals of each dose overlap; and 3) dose 2 only. Risk of the AESI occurring in these three categories of the risk intervals will be compared separately with the post-vaccination control intervals. Figure 4 presents some hypothetical examples in SCCS design with varying risk during the risk intervals and post-vaccination control intervals.

Figure 4. Hypothetical examples of SCCS design with varying risk during the risk interval and post-vaccination control intervals for two-dose vaccines

Note: The hypothetical risk interval following one dose is up to 28 days. However, the length of the risk and control intervals will vary for each AESI.

To assess the robustness of the case definition:

- Different clean window lengths will be explored.
 - Instead of using a fixed clean window length to define “incident AESI”, the study may consider clean windows that are longer than the length of the pre-defined clean windows (Table 3), constructed retrospectively from the anchoring date using all available data, for AMI, PE, DIC,

and ITP; however, extending the continuous enrollment to cover the full period of all available data is not required.

- In addition, a clean window shorter than the pre-defined clean window may be examined for AMI and PE as shown in Table 4 below.

Table 4. Alternative clean windows

AESI	Care Setting	Clean Window
Acute Myocardial Infarction (AMI)	IP	28 days ¹⁹
Pulmonary Embolism (PE)	IP, OP/ PB	183 days ²⁰

- To exclude chronic ITP among cases, all thrombocytopenia events in the pre-specified clean window (Table 3) will be excluded. Chronic ITP may be more common in the older adult population.²¹
- Alternative event definitions in Table 5 will be considered. Restriction to the inpatient setting is likely to increase the likelihood to capture acute events or relapse/exacerbation of the chronic events.

Table 5. Alternative AESI definitions

AESI	Care Setting
Acute Myocardial Infarction (AMI)	IP, primary diagnosis position
Type I AMI	IP
Type I AMI	IP, primary diagnosis position
Pulmonary Embolism (PE)	IP
Pulmonary Embolism (PE)	IP, primary diagnosis position
Disseminated Intravascular Coagulation (DIC)	IP
Disseminated Intravascular Coagulation (DIC)	IP, primary diagnosis position
Immune Thrombocytopenia (ITP)	IP
Immune Thrombocytopenia (ITP)	IP, primary diagnosis position

To assess the robustness of risk and control intervals, different lengths of the risk interval and the control interval will be explored with clinical input and consideration of empirical data from temporal clustering by plotting the distribution of incident AESI since vaccination and temporal scans to detect statistical clustering of events post vaccination. Given the potential carry-over effect, we will exclude a range of periods (e.g., 7, 14, and 21 days) after the end of the risk interval from contributing to the control intervals.

To assess the robustness of the analysis to potential violation of the assumption that exposures are independent of outcomes (e.g. AESI post first-dose may delay or preclude administration of the second-dose), a modified SCCS analysis will be conducted which adjusts for censored, perturbed or curtailed post-event exposures.²²

To assess the robustness of the analysis to the potential violation of the assumption that observation time is independent of outcomes (e.g. death post-AESI censors follow up time), a modified SCCS analysis will be conducted which removes the independence assumption.²³

To assess the robustness of the analysis to the potential under-capture of second doses administered by providers who do not submit insurance claims, a sensitivity analysis will be conducted removing projected second-dose exposed time potentially misclassified as control time among patients with only one observed dose. The empirical distribution of exposed time post-second dose will be assessed among patients with two doses, and the corresponding time will be excluded from the control time of patients with only one observed dose.

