5.5 Study Population

Eligible vaccinees are persons who received at least one dose of the COVID-19 vaccine and met the following inclusion/exclusion criteria regardless of the occurrence of the AESI. All eligible vaccinees will be used for the attributable risk (AR) calculation.

The case population will consist of COVID-19-vaccinated individuals with the AESI. Incident AESI will be defined as the first recorded event for an individual during the study observation period if there are no claims for the same AESI in the preceding pre-defined clean window. The clean window will be anchored on the date of the AESI and will begin a pre-defined number of days prior to the AESI as specified in Table 3. Sensitivity analyses will be conducted with different lengths of clean windows to assess the robustness of the incident AESI definition (Sections 5.7.2.1 and 5.7.3.1).

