5.5.1 Primary Analysis: SCCS with Post-vaccination Control Intervals

Eligible vaccinees should meet the following inclusion/exclusion criteria.

Inclusion criteria:

- (i) Medicare beneficiaries enrolled in Part A (hospital insurance) and Part B (medical insurance) during the study observation period, as well as during the clean window prior to the occurrence of the AESI.
 - Continuous enrollment will be required from the start of an AESI's clean window relative to the occurrence of the AESI through day 90 post-vaccination, the end of the study period, disenrollment, or death, whichever comes first.
- (ii) Received at least one dose of a COVID-19 vaccine during the vaccination period of interest. The end of the vaccination period is defined as the vaccination cut-off date.
 - The vaccination cut-off date will be selected for each outcome to reduce the possibility of bias due to incomplete capture of events.
- (iii) For case population only, had a record of the AESI diagnosis during the study observation period.

Exclusion criteria:

- (i) Less than 65 years of age at the start of observation period.
- (ii) Does not contribute follow-up time to both risk and control intervals. If individuals disenroll, or reach the end of the study period during the risk window prior to accumulating any time for post-vaccination control intervals, they will be excluded.
- (iii) Had COVID-19 vaccination patterns that do not conform to expectations for the analysis of interest, e.g., doses that occur within a short time period following another dose or have a higher than expected dose number; more specific rules will be determined once more data on vaccination patterns are available.
- (iv) Had a diagnosis of the AESI during the AESI-specific clean window (Table 3) or during alternate clean windows assessed in sensitivity analyses.
- (v) Received different COVID-19 vaccines for the first and second dose. Based on the preliminary assessment, such a scenario only occurred in approximately 0.12% of cases with an AESI.

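### The bootstrap for the attributable risk resamples only cases, which holds the case count fixed and makes the AR standard error slightly too small (about 1% to 5% at the planning rate ratios)

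*Protocol*

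**What the plan says.** Section 5.7.2 takes the excess as the model-fitted cases minus those expected if all observed time were control time. It then states: "The unadjusted AR is the excess number of AESI cases divided by the number of eligible vaccinations (or eligible follow up dose-years"). For precision it says that "The standard error (SE) of the unadjusted AR is estimated by bootstrap resampling 10,000 times", and that in each iteration "the study will sample the beneficiaries with AESI with replacement and repeat the AR calculation". The standard error is the square root of the variance of the 10,000 AR values. The number of draws per iteration is not given. The same section allows the AR to be compared with the AR after other vaccinations or other triggering exposures.

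Section 5.5 describes the population behind the denominator: "All eligible vaccinees will be used for the attributable risk (AR) calculation".

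**The concern.** The self-controlled model conditions on each person having had an event, so resampling cases is natural for the rate ratio. The AR is a different quantity: an absolute count divided by a number of vaccinations. If the same vaccinees could be followed again, both the split of cases between risk and control time and the total number of cases would change. A bootstrap that draws n cases from n cases reproduces the first source of variation and suppresses the second.

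What is at stake is the width of any interval placed around the AR, the absolute-risk figure that may be set beside those of other exposures. The shortfall grows with the rate ratio, so it is largest where the vaccine effect is largest.

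**Working it through.** **Inputs.** Rate ratios and case counts come from Table 6 (Section 5.8): AMI 1.42, n = 281 and 286; PE 1.54, n = 183 and 191; DIC 1.91, n = 79 and 89; ITP 1.44, n = 259 and 265, for 28 and 56 risk days respectively. The observation period is 90 days (Section 5.8). Assumptions: n draws per replicate, Poisson event counts, the same interval lengths for all cases, and a denominator large enough to be treated as a constant.

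**Reproducing Table 6.** Let r be risk days divided by observation days. The signed-root likelihood-ratio formula for the case series is

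- p = RR·r / (RR·r + 1 − r)
- A = 2[p·ln RR − ln(RR·r + 1 − r)]
- B = (ln RR)²·p(1 − p)/A
- n = (1.960 + 0.842·√B)²/A

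DIC with 28 risk days out of 91 (day 0 to day 90) gives A = 0.1005 and B = 1.035, so n = 78.9, rounded up to 79 as printed. All eight entries are reproduced exactly with 91 days, and within 2 with 90 days. The inputs are therefore understood correctly.

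**Variance of the excess.** Let k = risk days / control days, with x_R cases in risk time and x_C in control time. The protocol's excess reduces to E = x_R − k·x_C.

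- Case count fixed (n drawn from n): Var = n(1 + k)²·p(1 − p)
- Case count random (Poisson): Var = x_R + k²·x_C
- Difference: exactly E²/n

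**Worked case, DIC, 28 risk days of 90, n = 79.** k = 28/62 = 0.4516 and p = 53.48/115.48 = 0.4631, so x_R = 36.59, x_C = 42.41 and E = 17.43.

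- Fixed count: 79 × 1.4516² × 0.4631 × 0.5369 = 41.39, SE 6.43
- Missing term: 17.43²/79 = 3.85
- Random count: 36.59 + 0.4516² × 42.41 = 45.24, SE 6.73
- Ratio 6.43/6.73 = 0.956, so the SE is 4.3% too small before rounding.

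**All Table 6 rows (SE of the excess count).**

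| AESI | Risk days | SE, case count fixed | SE, case count random | Shortfall |
|---|---|---|---|---|
| AMI | 28 | 11.87 | 12.03 | 1.3% |
| AMI | 56 | 20.50 | 20.80 | 1.4% |
| PE | 28 | 9.66 | 9.85 | 2.0% |
| PE | 56 | 16.47 | 16.84 | 2.2% |
| DIC | 28 | 6.43 | 6.73 | 4.3% |
| DIC | 56 | 10.68 | 11.21 | 4.7% |
| ITP | 28 | 11.42 | 11.58 | 1.4% |
| ITP | 56 | 19.68 | 19.99 | 1.5% |

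Both variances scale with n, so the percentage depends on the rate ratio and the interval lengths, not on how many cases accrue. Using 91 days instead of 90 moves no shortfall by more than 0.03 percentage points. At RR 1.0, 1.1 and 1.2 the shortfall is 0, about 0.1% and about 0.4%.

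**Consequence and cross-check.** If a nominal 95% interval is formed as ±1.96 of this SE, the normal approximation puts its coverage at about 94.7% for AMI and 93.8–93.9% for DIC. In simulation, the mean case-only bootstrap SE divided by the true SD was 0.982–0.986 for AMI and 0.939–0.946 for DIC. That agrees with the formula in direction and approximate size. It is slightly lower for DIC, as expected of a bootstrap SE from fewer than 100 cases.

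**The case against.** The strongest reply is that the effect is negligible. The Table 6 rate ratios are unadjusted surveillance values, and at 1.1 to 1.2 the shortfall is at most 0.4%. The protocol already accepts larger uncertainties: up to 11% bias from claims delay (Section 5.3), and an interval of 0.71 to 0.87 around a PPV of 0.8 with 100 charts (Table 7). No hypothesis test uses the AR standard error. The number of draws per replicate is inferred, and bootstrap detail is often left to the analysis plan.

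Most of this stands, and it limits the point to a minor one. It does not remove it. The protocol itself fixes the sampling unit as cases only, and n from n is the ordinary reading. The other uncertainties do not cancel an error that always runs in one direction and costs almost nothing to correct.

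A reader might also infer that the AR denominator is wrong. Section 5.5 says "The clean window will be anchored on the date of the AESI", and Section 5.5.1 requires enrollment "as well as during the clean window prior to the occurrence of the AESI", yet vaccinees without an event have no such date. From this one might conclude that non-cases face no look-back and that the AR is biased low. The documents do not support that step. Section 5.5 defines eligible vaccinees as those who "met the following inclusion/exclusion criteria regardless of the occurrence of the AESI", and Section 5.5.1 restricts only inclusion criterion (iii) to cases, so the look-back is meant for everyone. Only the index date for non-cases is unstated. No share of vaccinees who would fail the look-back is given, so no bias can be computed.

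**Conclusion.** The point holds as a minor error in the AR standard error. With n-from-n resampling of cases, the variance of the excess count lacks E²/n, and the variance of the AR lacks that term divided by the squared denominator. At the protocol's own planning values the standard error is too small by about 1.3–1.5% for AMI and ITP, 2.0–2.2% for PE and 4–5% for DIC, and by nothing at a rate ratio of 1. This rests on the assumptions listed with the inputs, chiefly Poisson counts and n draws per replicate.

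Two stronger conclusions should be resisted. The rate ratio, its confidence interval and its p-value are not affected, because conditioning on the cases is correct there. Nor does the protocol give grounds for expecting a large error: it plans for no rate ratio above 1.91.

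**What to change.** In Section 5.7.2, let the case count vary in the AR bootstrap. Any one of these will do:

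- in each replicate, draw the number of cases from Poisson(n) and then sample that many cases with replacement;
- give each case an independent Poisson(1) weight, which is equivalent;
- resample all eligible vaccinees;
- keep the case-only bootstrap and add E²/n to the variance of the excess count before dividing by the squared denominator.

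The cost is one line of code and one sentence of text. At the Table 6 values the AR interval widens by about 1% to 5%. No primary result changes.

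As a clarification only, Sections 5.5 and 5.5.1 could name the index date at which the clean-window rules are applied to vaccinees without an AESI. Whatever date is chosen should apply to cases and non-cases alike for the AR. A different anchor for non-cases alone would mismatch numerator and denominator.

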5.7.3 Secondary Analysis: SCCS with Pre- and Post-vaccination Control Intervals

A similar conditional Poisson regression as the primary analysis (Section 5.7.2) will be conducted, except that control interval will include both pre- and post-vaccination time during the observation period.

When sample size permits, subgroup analyses by age group, sex, race/ethnicity, and nursing home residency status will be performed.

5.7.3.1 Sensitivity Analyses for the Secondary Analysis

To assess the healthy vaccinee effect, the incidence of the AESI prior to vaccination by day will be plotted to look for a potential drop in proximity to COVID-19 vaccination. If a reduction in the incidence of the AESI in the pre-vaccination period is detected, a different length of the pre-exposure window (e.g., 28 days) will be excluded based on empirical data.

To assess the robustness of risk and control intervals, the study will explore different lengths of the risk and control intervals with clinical input and consideration of empirical data from temporal clustering. For example, two times the length of the risk interval (Table 3) for the control interval is considered for greater statistical power although the likelihood of potential time-varying confounding is higher, given the longer observation period. To address the potential carry-over effect following the risk interval, a range of periods (e.g., 7, 14, and 21 days) after the end of the risk interval will be excluded from contributing to the control intervals.

